5.3 BIOMARKER AND RESEARCH METHODS

The technology platforms that are able to interrogate genomic structure and function are constantly in flux; therefore, the exact nature of the methodologies that will be employed will be assessed at the time that the samples are collected and ready for analysis. The protocol will be amended at that time, if needed, to describe the intended techniques prior to initiating the analyses

The following are technologies that are currently in use for each planned analysis:

5.3.1 Molecular Profiling

Immunohistochemical (IHC) analyses, including FISH and/or PCR testing, will take part in tumor tissue samples, including but not necessarily limited to CD2, CD3, CD4, CD5, CD7, CD8, CD14, CD16, CD20, CD25, CD38, CD45RA, CD45RO, CD56, CD62L, CD69, CD79a/CD79b, CD122, Foxp3, perforin, gamma/delta, CXCR3, CCR4, and NKG2D.

5.3.2 Immune Subset Analysis

Peripheral blood mononuclear cells (PBMC) will be assessed using multiparameter flow cytometry for immune subsets including but not necessarily limited to CD8+ T-cells, CD4+Foxp3- T-cells, Tregs, T_{ex}, Th1, Th2 and Th17+ CD4+ T-cells, NK cells and subsets, monocyte subsets, MDSC subsets. Assessment may include functional markers, i.e. PD-1, Tim-3, CTLA-4, PD-L1, HLA-DR, Ki67 and/or CD40.

5.3.3 ADCC Analysis

Peripheral blood mononuclear cells (PBMCs) should be isolated by Ficoll-Hypaque Density Gradient Centrifugation. The viable cells should be viably frozen and stored in liquid nitrogen. The ADCC assay will be performed on the same occasion for all samples of a given patient. Vials of frozen cells will be thawed using standard procedures 18 hours before the assay in accord with our experience with normal donors. 1.5 million of patient's PBMCs obtained before and on day 15 following IL-15 injection will be tested in aliquots as follows:

- Tested alone

- Tested with untreated PD-L1-expressing Raji cells, and with the Raji cells coated with avelumab for 5 hours.
- In addition, we may utilize an ATL cell line in addition to Raji cells. These cell populations will be stained with CD107, CD3, CD56, and CD94.

5.3.4 cfDNA/ctDNA and PBMC banking

Since the methods of molecular monitoring in the peripheral blood is an emerging field with numerous technologies under development, the storage of peripheral blood mononuclear cells (PBMC), serum, and plasma will all be performed allowing for future comparison of the different compartments for analytes that include cell-free circulating tumor DNA (ctDNA), and RNA sequencing of circulating tumor cells. Studies to be performed on these samples include: cfDNA/ctDNA for liquid genotyping as a non-invasive dynamic monitoring of disease as well as monitoring for individual molecular aberrations that herald progression or disease transformation; specifically, amplification and sequencing of the VDJ segment of the immunoglobulin receptor is planned. Germline DNA obtained from saliva, blood, or buccal mucosa will be used to discriminate somatic from germline mutations during cfDNA and ctDNA analyses. Keeping in mind a recent report of immune checkpoint inhibition in a patient with a solid tumor being associated with T-cell lymphomagenesis (50), and with our own group's experience with rapid progression in 3 patients with ATLL treated with ICI (22, 51), special attention will be paid to following T-cell clonality using amplification and sequencing of the complementarity determining region 3 (CDR3) in both cfDNA and banked PBMCs.

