2 ELIGIBILITY ASSESSMENT AND ENROLLMENT

2.1 ELIGIBILITY CRITERIA

2.1.1 Inclusion Criteria

2.1.1.1 Patients must have histologically or cytologically proven relapsed/refractory T-cell lymphoma other than adult T-cell leukemia/lymphoma (ATLL), angioimmunoblastic T-cell lymphoma (AITL), peripheral T-cell lymphoma T follicular helper phenotype (PTCL-TFH), or enteropathy-associated T-cell lymphoma (EATL), confirmed by the Laboratory of Pathology, NCI

2.1.1.2 Patients with CD30+ mycosis fungoides/Sézary syndrome (MF/SS) or CD30+ anaplastic large cell lymphoma (ALCL) must have relapsed after or become intolerant to treatment with brentuximab vedotin.

2.1.1.3 A formalin fixed tissue block or 15 slides of tumor sample (archival or fresh) must be available for performance of correlative studies. **NOTE:** Patients must be willing to have a tumor biopsy if prior tissue or adequate archival tissue is not available (i.e., post-enrollment and prior to treatment).

2.1.1.4 Disease must be measurable with at least one measurable lesion by RECIL 2017 or mSWAT criteria (see Section [6.3](#)), or have an abnormal clonal T-cell population detectable by peripheral blood flow cytometry

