2.2.3 Laboratory Evaluations

NOTE: Results from outside NIH are accepted.

- CBC with differential, platelets and reticulocyte count
- Chemistry panels (as noted) or specific analyte required for eligibility, including: Creatinine (i.e., Acute Care Panel); serum calcium, phosphate, magnesium and albumin (i.e., Mineral Panel); ALT, AST, total and direct (if required) bilirubin (i.e., Hepatic

Panel); 24-hour urine creatinine clearance (if needed to measure CrCl in cases where serum creatinine >1.5mg/dl); and LDH

- Serum Lipase and Amylase
- Coagulation panel, including: PT/INR and a PTT
- Thyroid function tests, including: thyroid stimulating hormone (TSH) with reflex free thyroxine (T4) per DLM policy
- Hepatitis B surface antigen (HBsAg), Hepatitis B core antibody, Hepatitis C antibody (HCV) [qualitative], HIV 1/2 antibody (qualitative) and HTLV-1/2 serologies (within 3 months) **NOTE:** For individuals with a positive hepatitis B core antibody, HBV DNA PCR will be performed to screen for subclinical infection.
- Urinalysis (with microscopic examination if abnormal)
- Antinuclear antibody (ANA), rheumatoid factor (RF) and anti-thyroid antibody
- Creatine phosphokinase (CPK), troponin
- Serum or urine pregnancy test (B-HCG) for women of childbearing potential
- Clonal T-cell receptor rearrangement by PCR

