10.4.9 Exploratory Analyses

The exploratory objectives such as seeking to identify potential biomarkers or T-cell clones in peripheral blood which are associated with response, will be assessed using descriptive statistics as well as non-parametric methods such as exact Wilcoxon rank sum tests. The analyses will be done without formal adjustment for multiple comparisons, but in the context of the number of tests performed.

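### The assay named for ctDNA disease monitoring in section 5.3.4 targets the immunoglobulin receptor, although every eligible patient has T-cell lymphoma

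*Combined protocol and SAP*

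**What the plan says.** Section 5.3.4 (cfDNA/ctDNA and PBMC banking) lists the studies to be done on the stored blood. The first is "cfDNA/ctDNA for liquid genotyping as a non-invasive dynamic monitoring of disease", together with watching for molecular changes that precede progression or transformation. The sentence closes by naming a method: "specifically, amplification and sequencing of the VDJ segment of the immunoglobulin receptor is planned".

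Later in the same paragraph, prompted by reports of lymphomagenesis and rapid progression under checkpoint inhibition, the section says that "special attention will be paid to following T-cell clonality", by CDR3 sequencing in both cfDNA and banked PBMCs.

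Elsewhere:

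- Section 2.1.1 restricts entry: "Patients must have histologically or cytologically proven relapsed/refractory T-cell lymphoma", with four subtypes excluded.
- Section 2.2.3 lists among the screening tests "Clonal T-cell receptor rearrangement by PCR".
- Section 10.4.9 gives as an exploratory aim the search for biomarkers or "T-cell clones in peripheral blood which are associated with response".
- Section 5.3 opens by treating the laboratory methods as provisional: "The protocol will be amended at that time, if needed, to describe the intended techniques prior to initiating the analyses".

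**The concern.** The word that introduces the immunoglobulin assay ties it to the disease-monitoring aim. It reads as the method chosen for that aim and not as an incidental extra. Yet immunoglobulin rearrangements mark B-cell clones, and no section gives a reason for following B-cell clones in this trial. A laboratory that took the sentence literally would spend required samples on a locus that does not identify the patients' lymphoma. The result could be matched neither to the T-cell receptor test at screening nor to the T-cell clone analysis in 10.4.9. What is at stake is the usefulness of one exploratory readout.

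**Working it through.** No figure is stated or implied, so there is nothing to recompute. The check sets the sections side by side.

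1. **Population.** Section 2.1.1 admits T-cell lymphoma only. The tumor clone in every enrolled patient is therefore a T-cell clone.

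2. **Clonality test at entry.** Section 2.2.3 and the study calendar (3.6) call for T-cell receptor rearrangement by PCR at screening. This matches point 1.

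3. **Assay named for monitoring.** Section 5.3.4 names the VDJ segment of the immunoglobulin receptor. This matches neither point 1 nor point 2.

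4. **Analysis that would use clonality data.** Section 10.4.9 names T-cell clones in peripheral blood. An immunoglobulin readout does not feed it.

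5. **Second assay in 5.3.4.** The plan also provides for "following T-cell clonality using amplification and sequencing of the complementarity determining region 3 (CDR3) in both cfDNA and banked PBMCs". This covers cfDNA as well as cells, so T-cell clone sequencing on the ctDNA specimens is planned. Two things are left unsaid. The receptor is not named, and CDR3 exists in immunoglobulin and T-cell receptors alike, so it has to be inferred from the reference to T-cell clonality. The sentence also does not say whether it replaces, repeats or supplements the assay in point 3.

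6. **Other ctDNA work.** Section 5.3.4 uses germline DNA to separate somatic from inherited mutations in the cfDNA and ctDNA analyses. Section 5.5.1 expects sequencing of ctDNA and possible exome sequencing for known lymphoma mutations. These routes do not depend on the receptor named.

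7. **Samples involved.** The table in section 5.1 marks the ctDNA draw as required at baseline and in follow-up, and as optional at cycle 1 day 8 and at day 8 of cycles 2 to 6. Its footnote limits follow-up draws to visits before progression. The accrual ceiling is 30 (10.2). Collection is into standard EDTA and Streck tubes (5.2.5), which does not depend on the receptor to be sequenced.

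8. **Endpoints.** Section 10.1 lists the MTD and treatment-emergent adverse events as primary, and response rate (overall and by PD-L1 expression), duration of response, and progression-free, event-free and overall survival as secondary. None uses ctDNA. Nor do the objectives in section 1.1.

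Points 1, 2 and 4 agree with one another, and point 3 is the exception. Points 5 to 8 bound the consequence.

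**The case against.** The strongest reply is that the paragraph corrects itself. The CDR3 sentence plans T-cell clone sequencing in cfDNA and gives it particular emphasis. One of its motives is rapid progression of a T-cell malignancy, which bears directly on disease monitoring. With 10.4.9 also naming T-cell clones, the intended analyte is clear enough, and the immunoglobulin phrase looks like a slip. Mutation-based ctDNA work is planned besides, and section 5.3 defers the exact methods until samples are ready.

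Most of this stands, and it rules out the stronger readings. A reader might infer that the trial would have no way to follow the tumor clone in ctDNA, that its monitoring aims could not be met, or that the ctDNA result would be lost in every patient. The documents do not support any of these, because the CDR3 plan and the mutation work remain. No sample is lost either, since collection is the same whichever receptor is sequenced.

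The reply does not remove the inconsistency. The immunoglobulin assay is still the one attached by name to disease monitoring, and the CDR3 sentence is presented as an addition to it. Section 5.3 introduces the listed methods as those currently in use for each planned analysis, and its amendment clause helps only if someone notices that an amendment is needed.

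**Conclusion.** The point holds as a mismatch between one named exploratory assay and the disease under study. The ctDNA monitoring method in 5.3.4 is directed at the wrong receptor and is not reconciled with the CDR3 sentence beside it, the screening test in 2.2.3 or the analysis in 10.4.9. Run as written, that assay would be uninformative for the tumor.

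The size is small. It concerns exploratory correlatives only, with no effect on the MTD, the adverse event endpoint or any secondary endpoint. It is not a failure of the ctDNA plan as a whole.

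The conclusion rests on two assumptions: that immunoglobulin rearrangement generally marks B-cell and not T-cell clones, which is general biology and not something the documents state; and that the sponsor has no separate, unstated purpose for B-cell receptor sequencing.

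**What to change.** In section 5.3.4, change the receptor named for VDJ sequencing from immunoglobulin to T-cell, and merge that sentence with the CDR3 sentence. Changing the one word alone would leave two overlapping T-cell receptor statements in the same paragraph. The merged text should describe one T-cell receptor (CDR3) sequencing assay, in cfDNA and PBMCs, that serves both disease monitoring and clonality surveillance.

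State that results are compared with the baseline T-cell receptor result where a clone is found. That qualifier is needed because 2.2.3 does not say that the screening PCR yields a trackable sequence in each patient, and it accepts results from outside NIH.

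If immunoglobulin sequencing is intended, keep it as a separate item and state what it is for.

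The cost is wording, through the kind of amendment that section 5.3 already foresees, with the same blood samples and the same kind of assay.

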5.3.5 DNA/RNA Sequencing

Genomic DNA and total RNA will be extracted from tumor samples using a Qiagen All-prep kit. For individual target genes that are recurrently mutated in T-cell malignancies, classical Sanger sequencing will be performed on PCR amplicons, using primers surrounding the known sites of mutation. To broadly assess mutations, next generation sequencing (e.g., on an Illumina HiSeq 2000 platform) will be employed, using a paired end sequencing strategy of libraries constructed from tumor DNA. DNA will either be sequenced in its entirety from a whole genome library or will be first enriched for exonic sequences using the Agilent Sure Select system, aiming for 30X or 100X average coverage per base, respectively. The sequence fragments will be mapped back to the genome using the BWA algorithm. Of sequences overlapping a particular base pair in the genome, the percent mutant calls greater than 20% with a minimum of 25X coverage will be considered as an arbitrary threshold for single nucleotide variants (SNVs). SNVs that are not present in the matched normal sample will be considered candidate somatic mutations.

A related technology, RNA-Seq, utilizes RNA from the tumor specimen to create a cDNA library for high-throughput sequencing. RNA-seq will be performed using Illumina kits followed by high-throughput sequencing on an Illumina HighSeq 2000 machine. The cutoffs for coverage and percent mutant calls mentioned above will also be used to identify putative SNVs. RNA sequencing will also be used to read out digital gene expression across the genome as described.

Recent advances in genomic technologies enable GEP at the single cell level, a distinct advantage over conventional GEP which cannot always distinguish tumor vs non-tumor gene expression. Single-cell approaches allow identification of the evolution of rare populations of resistant tumor cells, as well as identification of TME cells critical for the survival of the tumor. The Center for Cancer Research (CCR) has recently opened a single cell analysis core facility with expert staff headed by [name] within the CCR Genomics Core. This facility has the ability to take

purified viably frozen cells banked from patient biopsies and prepare them, using well-validated 10X Genomics technology, for single-cell RNA sequencing. This core is directly integrated with the NCI Sequencing core facility to provide high-quality, deep-sequencing of the single cell RNA-SEQ samples, as well as ‘first-pass’ data processing and analysis. Data will then be transferred to lymphoma researchers and bio-informaticians for further analysis of gene expression patterns and cellular population dynamics.

5.3.6 Other Analyses

Other analyses include the following:

- Cell analysis and histological (e.g., H&E), immunohistochemical review and analysis per standard and established research techniques (e.g., PD-1/PD-L1 expression [Dako], FISH for del(17p), and other IHC analyses in blood and tissue).
- Cytokine analysis (e.g., IL-6, IL-10, interferon beta, TNF-alpha)

5.3.7 Future Use

Any blood, tissue, or other products or portions leftover from other analyses will be stored for future research.

5.4 SAMPLE STORAGE, TRACKING, AND DISPOSITION

5.4.1 General

Samples will be ordered in CRIS and tracked through a Clinical Trial Data Management system. Should a CRIS screen not be available, the CRIS downtime procedures will be followed. Samples will not be sent outside NIH without appropriate approvals and/ or agreements, if required.

All specimens obtained in the protocol are used as defined in the protocol. Any specimens that are remaining at the completion of the protocol will be stored in the conditions described below. The study will remain open so long as sample or data analysis continues. Samples from consenting subjects will be stored until they are no longer of scientific value or if a subject withdraws consent for their continued use, at which time they will be destroyed.

If the patient withdraws consent the participant’s data will be excluded from future distributions, but data that have already been distributed for approved research use will not be able to be retrieved.

The PI will record any loss or unanticipated destruction of samples as a deviation. Reporting will be per the requirements in section [7.2](#).

5.4.2 Lymphoid Malignancies Branch – [name] Laboratory

Under the direction of [name], all samples processed by the laboratory will be uniquely barcoded, with data entered using a secure computerized database and backup hardcopy process per standard laboratory practice.

Samples are stored in labeled boxes in secured freezers (i.e., -20°C to -80°C, or other, as appropriate) according to stability requirements; these freezers are located onsite. Access to stored clinical samples is restricted and limited to research personnel for approved analyses only (as per the IRB approved protocol).

Upon completion of planned analyses by the [name] lab, leftover samples may be stored for future analyses at the Clinical Support Laboratory, Leidos Biomedical Research, Inc. in Frederick, MD (see below).

5.4.3 Clinical Support Laboratory, Leidos Biomedical Research, Inc. in Frederick, MD

The Clinical Support Laboratory, Leidos Biomedical Research, Inc.-Frederick, processes and cryopreserves samples in support of IRB-approved, NCI clinical trials. The laboratory is CLIA certified for anti-IL15 and certain cytokine measurements, and all laboratory areas operate under a Quality Assurance Plan with documented Standard Operating Procedures that are reviewed annually. Laboratory personnel are assessed for competency prior to being permitted to work with patient samples. Efforts to ensure protection of patient information include:

- The laboratory is located in a controlled access building and laboratory doors are kept locked at all times. Visitors to the laboratory are required to be accompanied by laboratory staff at all times.
- Hard copy records or electronic copies of documents containing patient information are kept in the locked laboratory or other controlled access locations.
- An electronic database is used to store information related to patient samples processed by the laboratory.
- The database resides on a dedicated program server that is kept in a central, locked computer facility.
- The facility is supported by two IT specialists who maintain up to date security features including virus and firewall protection.
- Program access is limited to specified computers as designated by the laboratory director. Each of these computers has a password restricted login screen.
- The database sample entry program itself is accessed through a password protected entry screen.
- Upon specimen receipt each sample is assigned a unique, sequential laboratory accession ID number. All products generated by the laboratory that will be stored either in the laboratory freezers or at a central repository facility are identified by this accession ID.
- Inventory information will be stored at the vial level and each vial will be labeled with both a sample ID and a vial sequence number.
- Vial labels do not contain any personal identifier information.
- Samples are stored inventoried in locked laboratory freezers and are routinely transferred to the NCI-Frederick repository facilities for long term storage.
- Access to stored clinical samples is restricted. Investigators establish sample collections under “Source Codes” and the Principal Investigator who is responsible for the collections specifies who has access to the collection.
- Specific permissions will be required to view, input or withdraw samples from a collection. Sample withdrawal requests submitted to approved laboratory staff by anyone other than the repository source code owner are submitted to the source code owner for approval. The repository facility will also notify the Source Code holder of any submitted requests for sample withdrawal.
- It is the responsibility of the Source Code holder (the NCI Principal Investigator) to ensure that samples requested and approved for withdrawal are being used in a manner consistent with IRB approval.

- The Clinical Support Laboratory does perform testing services that may be requested by clinical investigators including, but not limited to, immunophenotyping by flow cytometry and cytokine testing using ELISA or multiplex platforms.
- When requests are submitted by the NCI investigator for shipment of samples outside of the NIH it is the policy of the laboratory to request documentation that a Material Transfer Agreement is in place that covers the specimen transfer. The laboratory does not provide patient identifier information as part of the transfer process but may, at the discretion of the NCI investigator, group samples from individual patients when that is critical to the testing process.
- The NCI investigator responsible for the sample collection is responsible for ensuring appropriate approvals and/ or agreements are in place, if required, prior to requesting the laboratory to ship samples outside of the NIH.

5.4.4 Hematopathology Section of the Laboratory of Pathology (Tissue samples)

Archival and/or freshly collected and processed tumor tissue may be stored in the Hematopathology Section of Laboratory of Pathology until ready for planned and/or future research assays if the patient has agreed to allowing specimens to be used in future research studies. IRB approval will be obtained before using any samples to conduct studies that are not described within this protocol. Samples will be stored under conditions appropriate to the type of sample and processing (e.g., ambient or frozen).

Tissue that is given to the technician will be assigned an accession number (HP#) in the HP Case Logbook; sample tracking also takes place with a FileMaker Pro data base called HP Patient Information and Specimen Inventory. A Patient background sheet may be filled out and filed with any accompanying paperwork, with final reports and any supplemental reports that follow added as completed.

